9.4 STATISTICAL ANALYSES

9.4.1 GENERAL APPROACH

Continuous variables will be compared across groups using ANOVA or a Kruskal Wallis ANOVA depending on their distribution. Changes from baseline to time of measurement will be compared by analysis of covariance. Categorical variables will be measured by Fisher's Exact test. Correlations will be assessed by Spearman's coefficient.

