1 PROTOCOL SUMMARY

1.1 SYNOPSIS

Title: Vitamin C Infusion for Treatment In Sepsis and Alcoholic Hepatitis
Study Description: It is our long-term goal to identify relevant “druggable” targets for alcoholic hepatitis (AH) and to translate this knowledge in to effective strategies to prevent and treat AH. This proposal will focus on one key area of unmet need in the field i.e. those with alcoholic hepatitis who have active infection and sepsis.

Objectives: We hypothesize that in patients with sepsis and alcoholic hepatitis, a 96-hour infusion of vitamin C (ascorbic acid, AscA, 200mg/kg/24 hours) will improve hepatic function, be well tolerated, and will attenuate biomarkers of inflammation, vascular injury, and encourage fibrinolysis. To assess the efficacy of a 96-hour intravenous vitamin C infusion protocol (200 mg/kg per 24 hours) in patients with established alcoholic hepatitis (AH) and sepsis. In this course of performing this proof of concept phase II trial we will explore three hypotheses:

Hypothesis 1A: Vitamin C infusion will significantly attenuate hepatic dysfunction as measured by the model for end stage liver disease (MELD) score in patients with alcoholic hepatitis and sepsis.

Hypothesis 1B: Vitamin C infusion will be safe and tolerable in patients with alcoholic hepatitis and sepsis.

Hypothesis 1C: Vitamin C infusion will attenuate biomarkers of inflammation (C-Reactive Protein, procalcitonin), vascular injury (Thrombomodulin, Angiopoietin-2), while inducing the onset of a fibrinolytic state (Tissue Factor Pathway Inhibitor).

Endpoints:

Primary Endpoint: Change in MELD score at 96 hours as compared to baseline when compared to placebo.

Secondary Endpoints:

- SOFA Score and components at hours 48, 96, 168
 - PaO₂/FiO₂
 - SpO₂/FiO₂
 - Platelets
 - Total Bilirubin
 - Vasopressor status
 - Glasgow Coma Score
 - Creatinine or Urine Output
- CLIF-SOFA scores and components at hours 48, 96, 168
 - Total Bilirubin
 - Creatinine
 - Renal replacement therapy (yes/no)
 - West-Haven grade for hepatic encephalopathy (HE)
 - INR
 - Mean arterial pressure (MAP)
 - Use of vasopressors (yes/no)
 - PaO₂ or SpO₂
 - FiO₂
 - Use of mechanical ventilation (yes/no)
- Lille score
 - Age
 - Albumin (on admission)
 - Bilirubin (on admission, hour 96, 168)
 - Creatinine (on admission)
 - Prothrombin time (on admission)
- Maddrey Discriminate Function (MDF) at hours 96, 168
 - Prothrombin time (hours 96, 168)
 - Total bilirubin (hours 96, 168)

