9.2 SAMPLE SIZE DETERMINATION

We anticipate an average MELD of 29 on enrollment, with a standard deviation of 5 points, which is based on previous analysis of VCU patient data with alcoholic hepatitis and sepsis. If we assume an alpha of 0.05 and power of 80%, we will need to enroll 8 patients in each arm in order to detect a 25% decrease in MELD on day 4. Therefore, we will overpower and enroll 10 patients in each arm given uncertainties of power calculation. Changes from baseline to day 4 will also be compared across arms by Wilcoxon test. Power calculations were made with NQuery 4.0.

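### Lille score: only follow-up bilirubin can respond to treatment, and neither reading of the plan gives a workable adjusted analysis

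*Combined protocol and SAP*

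**What the plan says.** The synopsis (1.1, Secondary Endpoints) lists the Lille score with its inputs. Age, albumin and creatinine enter once, the two laboratory values as measured on admission. So does the clotting input: "Prothrombin time (on admission". Bilirubin is the only input with later values: "Bilirubin (on admission, hour 96, 168". The synopsis gives Lille as a score and does not call it a change.

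The table in Section 3 words the endpoint differently. It groups Lille with MELD-Na and MDF as changes versus placebo at hours 48, 96 and 168.

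No Lille-specific analysis appears anywhere. The general rule in 9.4.1 is "Continuous variables will be compared across groups using ANOVA or a Kruskal Wallis ANOVA depending on their distribution". The next sentence of 9.4.1 assigns changes from baseline to analysis of covariance, without naming covariates. The documents print no Lille formula.

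**The concern.** Five of the six inputs (age and the admission values of albumin, bilirubin, creatinine and prothrombin time) are settled before the first dose. If Lille is compared as a level without adjustment, all between-patient variation in those inputs stays in the error term, and any chance difference between arms passes into the estimated treatment effect. With 10 per arm such differences are not rare, and 6.3 names no prognostic stratification factor.

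At stake is the reading of one secondary endpoint of hepatic response. A real bilirubin response could go undetected within that score, or an arm that happened to be older or sicker on admission could look like a poorer responder.

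**Working it through.** **The plan's own figure.** Section 9.2 sizes the trial on MELD. Its inputs are "We anticipate an average MELD of 29 on enrollment", "with a standard deviation of 5 points", "If we assume an alpha of 0.05 and power of 80"%, and the target "in order to detect a 25% decrease in MELD on day 4". The difference is 0.25 × 29 = 7.25 points. The two-sided normal formula gives n = 2 × (1.960 + 0.842)² × (5/7.25)² = 7.47, rounded up to 8, which matches "we will need to enroll 8 patients in each arm". An exact two-sided t-test has power 0.769 at 8, 0.823 at 9 and 0.865 at 10 per arm. The figure reproduces, but it concerns MELD and says nothing about Lille.

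**The two readings of the plan.**

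| Reading | Source | Route under 9.4.1 | What is missing |
|---|---|---|---|
| Level, hours 96 and 168 | 1.1 | ANOVA or Kruskal-Wallis | any adjustment |
| Change, hours 48, 96 and 168 | Section 3 | ANCOVA | an hour-0 score to subtract or adjust for; a named covariate; an hour-48 bilirubin among the Lille inputs in 1.1 |

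The score needs a follow-up bilirubin. At hour 0 there is none, so a baseline Lille does not exist until someone defines it.

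**Power cost of not adjusting.** Let f be the share of the score's variance explained by its pre-treatment part. This is an assumption; the documents give no formula, weights or variances, so a range is shown.

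1. Setting: 10 per arm, two-sided 5%, noncentral t.
2. Under ANCOVA with one covariate (20 − 3 = 17 df), 80% power needs a difference of 1.33 residual SDs.
3. The residual SD is √(1 − f) of the total SD, so the same effect is 1.33 × √(1 − f) total SDs.
4. Unadjusted, that effect is tested with 18 df and noncentrality 1.33 × √(1 − f) / √(2/10).

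| f (assumed) | Effect in total SDs | Unadjusted power | Patients needed relative to ANCOVA, 1/(1 − f) |
|---|---|---|---|
| 0.1 | 1.26 | 76% | 1.1 |
| 0.3 | 1.11 | 65% | 1.4 |
| 0.5 | 0.94 | 51% | 2.0 |
| 0.7 | 0.73 | 34% | 3.3 |

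The 80% benchmark charges ANCOVA one degree of freedom but not the variance inflation from chance covariate imbalance. With that included, ANCOVA power is about 78%, so at f = 0.1 the gain is only about two points.

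**Chance imbalance.** In 40,000 simulated trials per value of f with no treatment effect, the unadjusted test rejected in about 5% (0.049 to 0.051 for f from 0.25 to 0.90). In about 26% of trials the arms differed by more than 0.5 SD of the pre-treatment part. Within those trials the rejection rate was 9%, 14%, 17% and 19% at f = 0.25, 0.50, 0.75 and 0.90.

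**The case against.** The strongest reply is that the plan does adjust. Section 3 calls Lille a change and 9.4.1 sends changes to ANCOVA. The synopsis also lists SOFA, CLIF-SOFA, MDF and MELD-Na without the word change, so its silence for Lille may be shorthand. This stands far enough to rule out a flat statement that Lille will be compared without adjustment. It does not rescue the plan, because for Lille, unlike those other scores, the listed inputs give no baseline value, and the ANCOVA cannot be run as written.

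A reader might also infer that the test would mostly compare pre-treatment characteristics. Five inputs out of six is a count, not a share of variance. The inference needs f above one half, and the documents give nothing from which to derive f.

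Nor is an unadjusted comparison biased. Randomisation holds its overall error rate at 5%; the higher conditional rates describe the unlucky trials within that 5%. And a bilirubin response has other places to show: total bilirubin at hours 48, 96 and 168 is a secondary endpoint, and bilirubin enters the primary MELD, which has its own ANCOVA (9.4.2). All of this stands and keeps the point small.

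Finally, the proposed covariate presupposes a Lille formula that the documents do not print. That is fair, and the fix asks for it.

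**Conclusion.** The point holds as a gap in specification with a cheap improvement available. Follow-up bilirubin is the only Lille input that can respond to treatment. The level reading gives an unadjusted test, and the change reading gives an ANCOVA with no baseline score and no covariate.

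The cost is lost precision and exposure to chance imbalance, not systematic bias. Its size rests on the assumed share f: small at 0.1 (76% against a nominal 80%), and substantial at 0.5 or above (51% or less). The figures also assume roughly normal scores, a linear relation between outcome and covariate, and all 20 patients contributing a score. One secondary endpoint is affected.

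**What to change.** Add to 9.4.1 that Lille at hour 96 and at hour 168 will each be compared between arms by ANCOVA, on the scale of the score's linear predictor, with one covariate: the same score recomputed with follow-up bilirubin set equal to admission bilirubin. That quantity is the pre-treatment part of the score and supplies the missing baseline. With this covariate in the model, the treatment estimate is identical whether the outcome is the level or the change from the covariate, since subtracting a covariate from the outcome alters only that covariate's own coefficient.

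State the Lille formula to be used. Reconcile 1.1 and Section 3 on level versus change and on hour 48: either drop hour 48 for Lille or add an hour-48 bilirubin to its inputs in 1.1.

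The cost is a short addition to the text, one derived variable from values the score already requires, and one degree of freedom. If the admission inputs explain almost none of the variance, ANCOVA loses a point or two of power. No visit or sample is added.

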 - PT control/reference level (assuming 12 seconds)
- Liver enzymes and function tests at hours 48, 96, 168
 - AST, ALT, total bilirubin, alkaline phosphatase, albumin
- MELD-Na Score at hours 48, 96, 168
 - INR, creatinine, bilirubin, sodium
- Documented tolerability at hours 24, 48, 96
 - Need for dose reduction, headache, dizziness, dry mouth, nausea, vomiting, flushing, rash, hypotension, treatment related adverse events
- Documented safety at hours 24, 48, 96
 - QTc Interval (EKG)
 - Crystalluria (Urinalysis with microscopy and pH testing)
- Serum Biomarkers
 - Procalcitonin, C-reactive protein, thrombomodulin, thromboelastography (TEG), Receptor for Advanced

Glycation End Products, Tissue Factor Pathway Inhibitor at study hours 0, 48, 96, 168 (When feasible)

- Ascorbate level at hour 0, 48, 96, 168 (When feasible)
- Need for escalation of support i.e. need for ventilator or pressor support when these are not needed at baseline
- ICU-free days at day 28
- All-cause mortality to day 28 and day 90
- Hospital-free days at day 90

Study Population: A total of 20 adult subjects with alcoholic hepatitis and suspected or documented sepsis will be enrolled in this study. All participants will be enrolled at the Virginia Commonwealth University Health System (VCUHS).

Phase: Phase II

[figure not shown]
Description of Sites/Facilities Enrolling Participants: Subjects will be recruited from the Emergency Department (ED), inpatient medicine unit admitted to the Digestive Health Service (DHS), and Intensive Care Units (ICU) at VCUHS.

[figure not shown]
Description of Study Intervention: Participants will be randomized to receive either intravenous Vitamin C (sterile L-ascorbic acid mixed in 5% dextrose in water) or placebo (5% dextrose in water). Active treatment will continue for 96 hours, discharge from study hospital, study withdrawal, or death, whichever comes first.

[figure not shown]
Study Duration: Years 1-4

[figure not shown]
Participant Duration: 90 days

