- Collection and monitoring of vital signs: blood pressure, temperature, heart rate, oxygen saturation
- Abbreviated physical exam
- Collection of blood for hematology, coagulation, clinical chemistry, biomarkers
- Document urine volume, urinalysis
- 12-Lead EKG
- AE review and reporting

Treatment Day 3 (Hour 72):

- Collection of concomitant medications (if applicable)
- Collection and monitoring of vital signs: blood pressure, temperature, heart rate, oxygen saturation
- Abbreviated physical exam
- Collection of blood for standard of care: hematology, coagulation, clinical chemistry
- Document urine volume
- 12-Lead EKG
- AE review and reporting

Treatment Day 4 (Hour 96):

- Collection of concomitant medications (if applicable)
- Collection and monitoring of vital signs: blood pressure, temperature, heart rate, oxygen saturation
- Abbreviated physical exam
- Collection of blood for SOC hematology, coagulation, clinical chemistry, and biomarkers
- Document urine volume, urinalysis
- 12-Lead EKG
- AE review and reporting

Study Day 7 (Hour 168):

- Collection of concomitant medications (if applicable)
- Collection and monitoring of vital signs: blood pressure, temperature, heart rate, oxygen saturation

- Collection of blood for SOC hematology, coagulation, clinical chemistry, and biomarkers

Study Day 28

- Phone call or chart review to document morbidity and mortality

Study Day 90

- Surviving subjects will be asked to come for a close out visit. However, this population is notorious for compliance issues and if they do not come in a phone call and chart review will be done along with assessment via national death register

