9 STATISTICAL CONSIDERATIONS

9.1 STATISTICAL HYPOTHESES

Our null hypothesis (H_0) is that intravenous infusion of vitamin C at 200 mg/kg/day will not result in decrease in MELD score from admission to day 4 when compared to placebo.

Our alternative hypothesis (H_1) is that intravenous infusion of vitamin C at 200 mg/kg/day will significantly reduce MELD scores at day 4 compared with MELD on admission in patients with alcoholic hepatitis and sepsis.

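### By default, Section 9.4.1 leaves mortality and other yes/no endpoints to Fisher's exact test, which at about 10 per arm gives up power that an exact unconditional test would keep

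*Combined protocol and SAP*

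**What the plan says.** The Synopsis (1.1) lists "All-cause mortality to day 28 and day 90" among the secondary endpoints, and Section 3 repeats it without a method. Section 9.4.1 gives general rules by type of variable: ANOVA or Kruskal-Wallis, analysis of covariance for changes from baseline, Spearman's coefficient, and "Categorical variables will be measured by Fisher's Exact test". Section 9.2 adds a Wilcoxon test for the change in MELD. No Kaplan-Meier, log-rank or Cox analysis appears anywhere.

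Section 4.4 has every subject followed to day 90. For those who miss the close-out visit, Section 8.1 provides that "a phone call and chart review will be done along with assessment via national death register".

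The only power statement concerns MELD: "If we assume an alpha of 0.05 and power of 80%, we will need to enroll 8 patients in each arm", with 10 per arm then to be enrolled. No error level, sidedness or power is given for mortality.

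**The concern.** Death by a fixed day is a categorical variable, so the Fisher rule is the only rule in the plan that reaches it. It also reaches the other binary endpoints, for example new need for a ventilator or pressors.

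Fisher's test conditions on both margins. With about 10 per arm few tables are possible, so the attainable significance levels lie far apart and the real error rate falls well below the nominal 5%. The unused part of the 5% is power given away, in a trial that has little to spare. Six deaths against one would be reported as non-significant. In addition, death dates should be obtainable from the planned follow-up, yet no planned analysis uses them: at day 90, a death on day 3 counts the same as one on day 85.

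**Working it through.** **The plan's own figure.** Section 9.2 states: "We anticipate an average MELD of 29 on enrollment, with a standard deviation of 5 points". A 25% decrease is 0.25 × 29 = 7.25 points. The normal-approximation formula n = 2(1.960 + 0.842)² × 5² / 7.25² gives 7.5, so 8 per arm, as stated. One-sided, the same calculation gives 6, so the stated figure fits a two-sided 5% test. I assume two-sided 5% for mortality too; the documents do not say.

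**Inputs for the check.** 10 per arm (Section 9.2) and two-sided 5% (assumed). Mortality rates are not in the documents and are assumed over a range.

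**True size of Fisher's test, 10 against 10.** Let R be the set of tables (a, b) with p ≤ 0.05. The rejection probability is Σ over R of Bin(a; 10, p₁) × Bin(b; 10, p₂), and the size is its maximum over p₁ = p₂. Fisher rejects at 5 or more deaths v 0, 7 or more v 1, 8 or more v 2, 9 or more v 3, and 10 v 4 or 5, plus the mirror images. At a common death rate of 50% each table has probability C(10,a)·C(10,b)/2²⁰. The rejected tables sum to 13,400/1,048,576 = 1.28%, which is the maximum. At common death rates of 20% and 30% the size is 0.76% and 1.19%.

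**Boschloo's test**, with the two-sided Fisher p-value as its statistic, also rejects 4v0, 6v1, 7v2, 8v3, 9v4 and 10v6 and their mirror images. These add 2 × (210 + 2,100 + 5,400 + 5,400 + 2,100 + 210) = 30,840, so the size is 44,240/1,048,576 = 4.22%, still under 5%. For 6v1, 7v2 and 8v3 deaths, Fisher gives p = 0.057, 0.070 and 0.070; Boschloo gives 0.023, 0.041 and 0.041.

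**Power, 10 against 10 (assumed death rates, placebo v vitamin C).** Fisher and Boschloo are by enumeration. The permutation log-rank is simulated with exponential survival times and complete follow-up. Two runs were made; where both covered a scenario, both results are shown.

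| Deaths | Fisher | Boschloo | Gain (points) | Permutation log-rank |
|---|---|---|---|---|
| 30% v 20% | 2.1% | 5.8% | 3.8 | not run |
| 30% v 10% | 5.7% | 14.3% | 8.6 | 8% (both runs) |
| 40% v 20% | 5.8% | 13.1% | 7.3 | 10% |
| 40% v 10% | 15.2% | 29.1% | 14.0 | 21% |
| 50% v 35% | 3.4% | 8.8% | 5.4 | not run |
| 50% v 25% | 8.6% | 18.2% | 9.6 | 15% |
| 50% v 20% | 13.2% | 25.4% | 12.2 | 24%, 25% |
| 60% v 30% | 12.3% | 24.8% | 12.5 | 27%, 23% |
| 60% v 20% | 25.3% | 42.5% | 17.2 | 42%, 44% |
| 60% v 10% | 47.4% | 65.9% | 18.5 | 63% |
| 70% v 20% | 42.6% | 62.2% | 19.6 | 63% (both runs) |

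Over a wider grid (placebo 20% to 80%, differences of at least 15 points) the Boschloo gain runs from 5 to 20 points, with a median of 12.

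**Other splits.** Blocks of 2, 4 or 8 (Section 6.3) and the per-protocol primary set (Section 9.3) mean that 10 against 10 is not assured. The gain is shown for the table's scenarios with differences of 20 to 50 points, omitting 40% v 20% and 50% v 25%.

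| Split (placebo v vitamin C) | Maximum Fisher size | Boschloo gain (points) |
|---|---|---|
| 9 v 10 | 2.1% | 3 to 10 |
| 9 v 9 | 2.1% | 5 to 10 |
| 8 v 8 | 2.1% | 2 to 10 |
| 9 v 11 | 2.8% | 0.5 to 14 |
| 8 v 9 | 3.4% | 0 to 9 |

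**Source of the loss.** Boschloo uses the same yes/no data as Fisher and recovers the power, so most of the loss is discreteness. With placebo mortality of 50% to 70% the permutation log-rank is within about 3 points of Boschloo. With placebo mortality of 30% to 40% it falls below Boschloo and gains only about 2 to 6 points over Fisher.

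**The case against.** The plan never says that mortality is reduced to yes/no or tested by Fisher. A reader might infer a deliberate choice, but Section 9.4.1 does not mention mortality. Fisher is only what the general rule yields when nothing else is specified. That objection stands, and the point is worded accordingly.

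The 1.3% ceiling and the largest gains belong to a two-sided test at exactly 10 against 10. Losing one placebo patient raises Fisher's power at 50% v 20% deaths from 13.2% to 18.0%. The gain also depends on effect sizes that the documents do not supply. This stands too, which is why ranges are given for other splits and smaller effects.

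Fisher's test is standard in small samples and keeps the error rate under 5%. Mortality is one of many secondary endpoints in a 20-patient proof-of-concept trial powered on MELD. In the scenarios tabulated, no test exceeds 66% power. All of this is true and limits the importance of the point, but it is not a reason to keep Fisher. At every split checked, Boschloo rejected every table that Fisher rejected, so switching loses nothing and the 5% level is still controlled.

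**Conclusion.** The point holds as a cheap improvement to secondary analyses. By default, mortality and other binary endpoints fall to Fisher's test. At exactly 10 against 10, two-sided 5%, its real error rate is at most 1.3%; at nearby splits the ceiling is about 2.1% to 3.4%. Boschloo's test would add about 4 to 20 points of power at 10 against 10 and about 0 to 14 at nearby splits. These gains rest on assumed death rates and an assumed two-sided test.

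Two stronger readings are not supported. One is that ignoring time of death causes the loss: the log-rank comparison shows that death times add little power beyond Boschloo, and their value here is mainly descriptive. The other is that the planned analysis risks false positives or invalidates a result: Fisher's test errs in the conservative direction, and the primary MELD analysis is not affected.

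**What to change.** In Section 9.4.1, replace Fisher's test with Boschloo's exact unconditional test for two-arm yes/no endpoints. State that it is two-sided at 5% and that the statistic is the two-sided Fisher p-value, because software differs in how it forms the two-sided version.

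For all-cause mortality, add time from randomisation to death through day 90, with Kaplan-Meier curves by arm and a permutation log-rank test. Censor subjects of unknown status at the date last known alive. Keep the day-28 and day-90 proportions with exact confidence intervals.

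The cost is a few sentences before unblinding and slightly more analysis work. No new procedure is needed, provided that the date of death and the date last known alive are recorded from the follow-up already planned. One downside is that the log-rank test addresses survival time and not risk at a fixed day, so the fixed-day proportions must stay in the report. Adopting Boschloo alone would leave the endpoints unchanged.

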9.4.2 ANALYSIS OF THE PRIMARY EFFICACY ENDPOINT(S)

Change in MELD from baseline to day 4. Changes from baseline to time of measurement will be compared by analysis of covariance.

We will use the following MELD formula:

Original MELD Score = $(0.957 * \ln(\text{Serum Cr}) + 0.378 * \ln(\text{Serum Bilirubin}) + 1.120 * \ln(\text{INR}) + 0.643) * 10$
(if hemodialysis, value for Creatinine is automatically set to 4.0)

Note: If any score is <1, the MELD assumes the score is equal to 1.

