5 STUDY POPULATION

5.1 INCLUSION CRITERIA

The inclusion and exclusion criteria listed for the CITRIS-AH trial are listed below. The definitions of alcoholic hepatitis and severe sepsis for this study are derived and defined as previously published in the reference literature.

Patients must have a diagnosis from the attending physician or hepatologist of definite or probable alcoholic hepatitis based on NIAAA criteria (2) and suspected or proven infection, and meet 2 out of 4 of the criteria for Systemic Inflammatory Response (SIRS) due to infection or be accompanied by at least 1 criterion for sequential organ failure assessment (SOFA):

1. Alcoholic hepatitis:
 - a. Definite NIAAA alcoholic hepatitis
 - i. Clinical diagnosis and histological confirmation of features of alcoholic hepatitis
 1. Histological diagnosis: liver biopsy with steatohepatitis, lobular inflammation, Mallory-Denk bodies, hepatocyte degeneration or ballooning, “chicken-wire” or portal fibrosis
 2. Clinical diagnosis:
 - a. Chronic alcohol use for at least 5 years (may be intermittent abstinent)
 - b. >1 standard drink per day in women and >2 in men
 - c. AUDIT score >15
 - d. Heavy alcohol use for at least 6 months
 - i. “Heavy use” = average >3 drinks per day (40g) for women and average 4 drinks (50-60g) per day for men
 - e. Onset of jaundice within the past 8 weeks
 - f. Less than 8 weeks of abstinence before onset of jaundice
 - g. Serum bilirubin >3 mg/dL
 - h. AST >50
 - i. AST/ALT ratio >1.5 and levels <400 IU/L
 - b. Probable NIAAA alcoholic hepatitis criteria
 - i. Clinical diagnosis based on heavy alcohol use >5 years
 - ii. Active alcohol use until 4 weeks prior to presentation
 - iii. average >3 drinks per day (40g) for women and average 4 drinks (50-60g) per day for men
 - iv. Sudden onset or worsening of jaundice (bilirubin >3 mg/dL) within past 60 days
 - v. AST/ALT ratio >1.5 and levels <400 IU/L
 - vi. Absence of other causes of liver disease
 1. Negative autoimmune markers (ANA < 1:160, SMA <1:80)
 2. Negative viral hepatitis markers (HAV A IgM, HBV sAg, HBV c IgM, HCV Ab, HCV RNA)
 3. No recent exposure to drugs with DILI potential, as determined by attending physician or hepatologist medication review
 - c. Patients with potential cofounders may be offered transjugular liver biopsy to assess for histological characteristics of alcoholic hepatitis and ruling out other features of chronic liver disease as a part of standard of care

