2. Suspected or proven infection: (e.g., thorax, urinary tract, abdomen, skin, sinuses, central venous catheters, and central nervous system.)
3. The presence of a systemic inflammatory response: Defined as: fever: >38°C (any route) or hypothermia: <36°C (core temp only), tachycardia: heart rate > 90 beats/min or receiving medications that slow heart rate or paced rhythm, leukocytosis: >12,000 WBC/μL or leukopenia: <4,000 WBC/μL or >10% band forms. Respiratory rate > 20 breaths per minute or PaCO₂ < 32 or invasive mechanical ventilation.
4. The presence of sepsis associated organ dysfunction as assessed by SOFA: (any of the following thought to be due to infection)
 - a. Sepsis associated hypotension (systolic blood pressure (SBP) < 90 mm Hg or an SBP decrease > 40 mm Hg unexplained by other causes or use of vasopressors for blood pressure support (epinephrine, norepinephrine, dopamine =/> 5mcg, phenylephrine)
 - b. Arterial hypoxemia (PaO₂/FiO₂ ≤ 300) or supplemental O₂ > 6LPM.

- c. Lactate > upper limits of normal laboratory results
 - d. Urine output < 0.5 ml/kg/hour for > two hours despite adequate fluid resuscitation
 - e. Platelet count < 100,000 per mL
 - f. Coagulopathy (INR > 1.5)
 - g. Bilirubin > 2 mg/dL
 - h. Glasgow Coma Scale < 11 or a positive CAM ICU score
5. Negative urine or serum toxicology and acetaminophen drug screen

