5.2 EXCLUSION CRITERIA

1. Known allergy to Vitamin C
2. Inability to obtain consent
3. Age < 18 years
4. No indwelling central or peripheral venous or arterial catheter in patients requiring insulin in a manner that requires glucose being checked more than twice daily (e.g. continuous infusion, sliding scale)
5. Presence of diabetic ketoacidosis
6. Patient or surrogate or physician not committed to full support (not excluded if patient would receive all supportive care except for cardiac resuscitation);
7. Pregnancy or breast feeding (as documented by urine or serum pregnancy testing)
8. Moribund patient not expected to survive 24 hours
9. Active or history of kidney stone
10. History of chronic kidney disease, stage IIIb or above
11. History of glucose-6-phosphate dehydrogenase (G6PD) deficiency
12. Active malignancy, except non-melanoma skin cancer
13. Uncontrolled upper or lower gastrointestinal bleeding
14. Possible alcoholic hepatitis or other confounding cause of acute hepatitis such as viral, metabolic, autoimmune
15. History of decompensated cirrhosis as indicated by variceal bleeding within 3 months, tense ascites, or hepatocellular carcinoma (HCC)
16. History of liver or other organ transplantation
17. Initial ALT or AST greater than 5 times the upper limit of normal
18. Positive urine or serum toxicology screen and acetaminophen level
19. Non-English speaking
20. Ward of the state (inmate, other)

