8.3.5 ADVERSE EVENT REPORTING

Investigators will report all unanticipated problems that involve risk or harm to a research participant AND was not anticipated or foreseen (e.g., not described in the consent form) AND is probably or definitely related to or caused by the research to the IRB in the required reporting time frame. The IRB at VCUHS will be notified within 5 business days of receiving notice of the unanticipated problem.

VCU will report all unanticipated problems, defined as problems that involve risk or harm to a research participant AND was not anticipated or foreseen (e.g., not described in the consent form) AND is probably or definitely related to or caused by the research, to the DSMB within 7 calendar days of the being notified of the event.

Investigators will also determine if the serious adverse event is unexpected for Vitamin C. Unexpected for Vitamin C is defined as any event not listed in the Vitamin C package insert. If the investigator determines that any serious and study-related adverse event is unexpected for Vitamin C, the FDA will be notified within 7 calendar days. Such events may also meet the definition of Unanticipated Problems as described below.

Examples of untoward clinical occurrences, or disease-related events (DREs) that are expected in the course of AH include: 1) transient hypoxemia, 2) agitation, 3) delirium or hepatic encephalopathy, 4) nosocomial infections, 5) skin breakdown, 6) gastrointestinal bleeding, 7) acute kidney injury, and 8) worsening of hepatic function. Such events, which are often the focus of prevention efforts as part of usual ICU care, will not be considered reportable adverse events unless the event is considered by the investigator to be associated with the study drug or procedures, or unexpectedly severe or frequent for an individual patient sepsis and AH. Examples of unexpectedly frequent untoward clinical occurrences would be repeated episodes of unexplained hypoxemia. This would be in contrast to an isolated episode of transient hypoxemia (e.g., SpO₂ ~85%), related to positioning or suctioning. This latter event would not be considered unexpected by nature, severity or frequency. These events will be captured in the eCRF.

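### The primary-endpoint MELD rule fixes creatinine at 4.0 on hemodialysis but sets no ceiling off dialysis, so new dialysis from a baseline above 4.0 scores as improvement on the creatinine term

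*Combined protocol and SAP*

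**What the plan says.** Section 9.4.2 defines the primary endpoint as the change in MELD from baseline to day 4, compared by analysis of covariance. It writes out the formula and adds two scoring rules. For dialysis: "if hemodialysis, value for Creatinine is automatically set to 4.0". For low values: "If any score is <1, the MELD assumes the score is equal to 1". No section gives an upper limit for creatinine in a patient who is not dialysed. The MELD-Na entry in the synopsis (1.1) only lists its components.

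On eligibility, one of the alternative organ-dysfunction criteria in 5.1 is "Urine output < 0.5 ml/kg/hour for > two hours despite adequate fluid resuscitation". The renal exclusions in 5.2 are "Active or history of kidney stone" and "History of chronic kidney disease, stage IIIb or above". Neither sets a creatinine limit or excludes acute kidney injury. Section 8.3.5 counts "7) acute kidney injury, and 8) worsening of hepatic function" among the events expected in this disease.

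The schedule of activities (1.3) records creatinine and dialysis use at hours 0, 48, 96 and 168. The CLIF-SOFA components in 1.1 refer to renal replacement therapy in general, whereas 9.4.2 refers only to hemodialysis.

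**The concern.** Creatinine is scored on two different scales. Off dialysis its logarithm can rise without limit; on dialysis it is fixed at ln(4.0). A patient who enters with creatinine above 4.0 and then needs dialysis moves from the open scale to the fixed one, and the score falls. A worse renal course is recorded as a gain on the sole primary endpoint.

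With 10 patients per arm, a few scores of the wrong sign are visible in the result. If the case is not settled in advance, whether to cap would be decided when the data are in hand. Whether continuous renal replacement counts as hemodialysis is open in the same way.

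**Working it through.** **Inputs.** From 9.4.2: creatinine coefficient 0.957 × 10 = 9.57 points per unit of ln(creatinine), dialysis value 4.0, floor 1. From 9.2: mean MELD 29, SD 5, 25% decrease, alpha 0.05, power 80%, 8 per arm needed and 10 enrolled. The baseline creatinine values below are assumed, because the documents give no distribution.

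**The plan's own figure.** The target is 0.25 × 29 = 7.25 points. With a two-sided normal approximation, n = 2 × (1.96 + 0.84)² × 5² / 7.25² = 7.5, rounded up to 8 per arm. This matches 9.2 and is not in dispute.

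**Effect in one patient.** With bilirubin and INR held constant, the change on starting dialysis is 9.57 × ln(4.0 / baseline creatinine).

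| Baseline creatinine | Change in points | Share of 7.25 | Change with a 4.0 cap |
|---|---|---|---|
| 5 | 9.57 × ln(4/5) = -2.14 | 29% | 0 |
| 6 | 9.57 × ln(4/6) = -3.88 | 54% | 0 |
| 8 | 9.57 × ln(4/8) = -6.63 | 91% | 0 |

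At or below 4.0 the sign is right: from 3.0, 9.57 × ln(4/3) = +2.75; from 2.0, 9.57 × ln(4/2) = +6.63.

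The fall in total MELD can be offset. At baseline 5 this takes a 1.21-fold rise in INR or a 1.76-fold rise in bilirubin. At baseline 6 it takes 1.41-fold or 2.79-fold.

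**Effect on the arm mean.** One patient at baseline 6 shifts a 10-patient mean by 3.88/10 = 0.39 points. Two at baseline 8 in the same arm shift it by 2 × 6.63/10 = 1.33. The unadjusted standard error of the arm difference is 5 × √(2/10) = 2.24.

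**Effect on the test.** Simulated ANCOVA with 10 per arm, assumed SD 5 and baseline-to-day-4 correlation 0.5, at least 20,000 trials per case. The artefact is added to the change score of the affected patients. Their higher baseline MELD is not modelled.

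| Affected patients | Placement | Power at 7.25 | Rejection rate under the null |
|---|---|---|---|
| None | – | 0.93 | 0.05 |
| One, baseline 6 | random | 0.92 | 0.05 |
| Two, baseline 8 | random | 0.87 | 0.05 |
| Two, baseline 8 | both placebo | 0.74 | 0.07 |
| Two, baseline 8 | both vitamin C | 0.97 | 0.07 |

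With random placement the mean estimate under the null is about 0. The chance that two given patients both fall in placebo is 10/20 × 9/19 = 0.24, and the same for vitamin C.

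**The case against.** The strongest reply is that the case is narrow. It needs baseline creatinine above 4.0, no dialysis at Hour 0, and dialysis at hour 96. The low-urine-output criterion does little to show that such patients will enroll: it concerns urine output rather than creatinine, and it is one of several alternatives. Most patients will qualify without it, since the alcoholic hepatitis definitions require bilirubin above 3 mg/dL (for definite disease, "Serum bilirubin >3 mg/dL") while the organ-dysfunction list asks only for more than 2. This stands: the documents show that such patients may enter, not that many will.

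It can also be said that the Wilcoxon comparison in 9.2 and the separate creatinine and renal replacement components in 1.1 give protection. They help in part. Ranks limit the influence of one patient, and the components would reveal the cause. But the Wilcoxon test uses the same mis-scored change, and neither corrects the ANCOVA. The label of the formula as the original MELD might be meant to imply a conventional ceiling, but none is written.

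A reader might infer two stronger points, and the documents support neither.

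- **Inflated type I error.** The 0.07 arises only when both affected patients are placed in one arm by assumption. Type I error is averaged over randomization, and there it stays at 0.05. The power of 0.74 is likewise a selected worst case.
- **Affected patients close to typical at entry.** This would follow if "Coagulopathy (INR > 1.5" were an entry threshold, since bilirubin 3 and INR 1.5 give a modest MELD even with high creatinine. It is one optional criterion, and 5.1 sets no minimum INR.

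**Conclusion.** The omission is real and worth correcting. Applied as written, 9.4.2 gives a wrong-direction creatinine score, 29% to 91% of the design effect for baselines of 5 to 8, in any patient with baseline creatinine above 4.0 who is on dialysis at hour 96. The sign is certain for the creatinine term; for total MELD it depends on bilirubin and INR.

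For the trial as a whole the likely consequence is modest. If dialysis is unrelated to treatment, the artefact adds noise and not bias: one patient at baseline 6 hardly matters, and two at baseline 8 cost about 0.06 in power. The estimate moves by about 1.3 points only if both fall in the same arm. Bias in expectation requires dialysis use to differ by arm, which cannot be judged from the documents. These sizes rest on assumed creatinine values, an assumed number of patients, SD 5 and correlation 0.5. The sample size is unaffected.

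**What to change.** In 9.4.2 add: 'Creatinine above 4.0 is set to 4.0 at every time point, on or off dialysis.' Also state that the existing dialysis value applies to renal replacement therapy of any modality, within a short window before each score, with the window fixed before unblinding. Leave the ANCOVA and the analysis sets as they are.

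The window should be neither the moment of sampling alone nor the whole period back to Hour 0, because both extremes create new errors:

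- **Moment of sampling only.** Baseline 3.5, intermittent dialysis at hour 84, creatinine 2.0 at hour 96 with no dialysis running. The score is 9.57 × ln(2.0/3.5) = -5.4, a false improvement. With the dialysis value applied it is 9.57 × ln(4.0/3.5) = +1.3.
- **Back to Hour 0.** Baseline 2.0, brief early dialysis, recovery to 1.0. The score is +6.6 instead of 9.57 × ln(1/2) = -6.6.

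The cost is small. Creatinine and dialysis use are already scheduled at each scoring hour. The documents do not say whether dialysis timing is captured, so it may have to be taken from the chart. The real downside is lost information above 4.0 without dialysis: a move from 6 to 4, or from 4 to 6, counts as 0 instead of -3.9 or +3.9. A rise from 2.0 to 6.0 scores +6.6 with or without dialysis, where the present rule gives 9.57 × ln(6/2) = +10.5 without it. The cap makes the two groups consistent; it does not recover the full extent of severe worsening.
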